6.7.1 Primary Safety Analysis

The use of study treatment will be considered safe if the proportion of SAEs in the active rTMS group is not statistically significantly higher than that in the sham group. Number of subjects with SAEs and TESAEs will be summarized by group and compared using a Chi Square test.

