2013, Harvey RL, manuscript in preparation]. This includes the use experience in the NICHE multicentre trial in which no device related SAE occurred in the 3448 therapy sessions performed in 199 patients using the same trial device and protocol as the present trial. In addition, the independent Data and Safety Monitoring Board (DSMB) monitoring the NICHE trial identified no safety related concerns during the trial.

Based on the fact that the rTMS train used in the present clinical trial falls comfortably and with a wide margin (50%) within the consensus safety guidelines and the lack of side-effects in the relatively extensive literature specific to the study population in the present trial the rTMS paradigm of the present study can be considered a non-significant risk application.

Potential adverse effects

There are, however, potential risks of seizures, hearing loss, immunological and neuropathological changes, as described below.

Microvascular Changes

Studies of prolonged exposure to TMS were performed in animal models. Microvascular changes in the cortex were found in rats exposed to over 100 pulses at 2.8 Tesla, but these findings were not evident in rabbits exposed to 100- 200 pulses per day at 2.4 Tesla over 30-42 days [Nishikiori 1996], nor were they seen in rabbits exposed to 1000 pulses at 2.0 Tesla over a period of months [Counter 1993]. Furthermore, rats exposed to 50-60 1.9- Tesla pulses delivered over 15 minutes had no significant changes in blood-brain barrier permeability [Ravnborg et al. 1990].

Seizure Activity

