5.2.3 Randomization

Randomization will occur using a random number generator programmed to randomize patients to rTMS vs Sham TMS in a 1:1 ratio such that approximately 30 patients will be randomized to treatment and 30 patients randomized to sham. Randomization will be done separately for each participating site so that the 1:1 ratio for treatment arms will be attained at each participating site. In addition, for each site the randomization will be performed in randomly occurring blocks of 3 to 6 patients. Further, patients who have suffered a stroke 3 to 6 months before the trial will be randomized separately from those who have suffered stroke more than 6 months (maximum 12 months) earlier.

The groups differ only as to the rTMS protocol they receive during the study. The groups are : sham rTMS (900 pulses at 1Hz frequency), and active NBS-rTMS (900 pulses at 110% of motor threshold, 1Hz frequency).

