6.1 POWER ANALYSIS AND BORROWING DATA FROM NICHE-TRIAL ACTIVE TRIAL ARM RESULTS

In a pilot study of 30 patients of whom 20 were randomized to active NBS-rTMS and 10 to sham-rTMS, 84% of the active NBS-rTMS group and 50% of the sham rTMS group attained clinically significant improvement of at least 5 points on the Fugl-Meyer score [Harvey RL 2009, Harvey RL, unpublished].

Similarly, in the completed multi-centre trial (NICHE-trial, NCT02089464) of 199 subjects using the same trial device but different sham coil design, 72% of subjects with ischemic stroke receiving active NBT-rTMS attained clinically significant improvement of at least 5 points on the Fugl-Meyer score [Harvey RL, manuscript in preparation] while the average expectation of NICHE trial site principal investigators of subjects improving was 36%.

Based on this data and sample size calculations utilizing significance level of 0.05 for p, we estimate that enrolling 60 patients need to be recruited to the present study to rule out the null hypothesis that there is no difference between active NBT-rTMS and sham-rTMS with 81% power. This assumption is based on the pilot study finding of 33% difference in responder rate between groups in favour of the NBS-rTMS group and 36% difference in the actual vs expected responder rate in patients with ischemic stroke in NICHE. However, since the active treatment arm of the present trial and the active trial arm of NICHE are treated in a completely identical manner (the same NBT device, same active rTMS protocol, the same standardized occupational therapy protocol as in NICHE, the same number of therapy sessions in the same schedule at the same trial sites, etc) this allows pooling of the data obtained in the NICHE active trial arm to the data obtained in the active trial arm in the present trial. As in NICHE there were 88 subjects with ischemic stroke receiving active NBT-rTMS. Combining their data with that of the present trial will lead into a trial population of approximately 118 subjects receiving active treatment (88 from NICHE + 30 from the present trial) and approximately 30 subjects receiving sham treatment (all from the present trial). The study power in this population is sufficient to rule out the null hypothesis with 96% power.

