6.5 SIGNIFICANCE LEVEL

Unless otherwise noted, all statistical analyses will be conducted with a significance level (α) of 0.05 and utilize two-sided testing.

Since the ARAT test has potential to be used for labelling purposes, a Bonferroni adjustment will be employed. A significance level (α) of 0.025 will be used for this secondary analysis only. All other secondary analyses will use $\alpha = 0.05$ as they are not to be used for any labeling purpose.

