- ensure the confidentiality of the trial data and the results of monitoring; and,
- assist Sponsor by commenting on any problems with study conduct, enrollment, and sample size and/or data collection.

All subjects will be monitored by a member of study staff during the study visits. All cases performed during a calendar month will be reviewed at the end of that month to monitor for any potential adverse effects from the subjects' participation in the study.

ADVERSE EVENT REPORTING GUIDELINE

Serious_adverse events will be reported to the IRB and the sponsor verbally within 24 hours, followed by a full written report within 10 working days. All other adverse events will be summarized in the progress report at Continuing Review by IRB and evaluated by DSMB. All adverse events will be assessed for their relationship to the study device or procedure by DSMB.

Throughout the study, adverse events and concomitant medications will be monitored and recorded. All Serious Adverse Events will be captured and assessed. All Serious Adverse Events will be reported as event and patient based count.

ADVERSE EVENT

An adverse event (AE) is any undesirable clinical experience (any sign, symptom, illness, abnormal laboratory value or other medical event) that occurs in a subject (or an event that worsens during the course of the study) and that could possibly be associated with the investigational product, procedure or medications required by this protocol. An adverse event may result from a device failure if an undesirable clinical event occurs. In this study, subjects should be encouraged to report AEs spontaneously.

Adverse event information will be collected throughout the study. Data collection will include event type, date of onset severity relationship to the procedure and investigational device, and event resolution, if any, at the conclusion of the study. All events will be followed for the duration of the study until they are resolved or their status at study conclusion is explained.

Serious Adverse Event

Each study investigator must decide whether an adverse event meets the definition of a "serious" adverse event. The regulatory definition of a serious adverse event (SAE) is an event that is fatal or life-threatening, results in persistent or significant disability, requires intervention to prevent permanent impairment, results in hospitalization (or prolongation of a hospitalization) or results in congenital anomaly or malignancy.

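### Section 6.7.1 declares the treatment safe whenever the SAE difference is not statistically significant; at about 30 per arm, 3 vs 0, 5 vs 1 or 7 vs 2 subjects with SAEs would all pass

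*Combined protocol and SAP*

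**What the plan says.** Section 6.7.1 sets the criterion: "The use of study treatment will be considered safe if the proportion of SAEs in the active rTMS group is not statistically significantly higher" than in the sham group. It names the test: "Number of subjects with SAEs and TESAEs will be summarized by group and compared using a Chi Square test". It does not say whether a continuity correction applies, and it states no significance level or sidedness of its own. The general rule in section 6.5 therefore applies, a significance level "of 0.05 and utilize two-sided testing".

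Section 5.2.3 gives the arm sizes: "approximately 30 patients will be randomized to treatment and 30 patients randomized to sham". Section 6.3 defines the Safety population as all treated subjects, analysed as treated. Section 6.1 describes borrowing of NICHE data for the efficacy analysis only, so the SAE comparison stays at about 30 vs 30.

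The sample size is justified in section 6.1 by responder rates: "This assumption is based on the pilot study finding of 33% difference in responder rate between groups", together with the NICHE actual-versus-expected responder difference. SAEs play no part in it.

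On prior SAE experience, section 2.2 reports for NICHE that "no device related SAE occurred in the 3448 therapy sessions performed in 199 patients". The SAE definition in section 7.0 is wider than device-related events: among other criteria, an event qualifies if it "results in hospitalization (or prolongation of a hospitalization").

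**The concern.** A non-significant test shows only that the data are compatible with no difference. They may be just as compatible with a large excess of SAEs. A safety claim needs either a stated margin that the upper confidence limit must stay below, or a plain statement of how large an excess has not been excluded. Section 6.7.1 has neither.

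The rule also rewards lack of information: the fewer subjects treated, the harder significance is to reach and the easier the safe verdict becomes. If the rule is followed as written, the primary safety conclusion could be that treatment is safe alongside a clear numerical excess of SAEs on active rTMS. A reader would take as shown something the trial did not test.

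**Working it through.** **Inputs.** 30 subjects per arm (5.2.3); chi-square test on subjects with an SAE (6.7.1); two-sided 0.05 (6.5). The documents state no all-cause SAE rate, so the true rates in step 3 are assumptions, shown as a range.

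**Step 1: the plan's own power figure.** For two proportions, power = Φ{[|p₁ − p₂|√n − 1.96√(2p̄(1 − p̄))] / √[p₁(1 − p₁) + p₂(1 − p₂)]}. With n = 30 and the pilot rates of 84% vs 50%, p̄ = 0.67 and power = Φ[(1.862 − 1.303)/0.620] = Φ(0.901) = 81.6%. NICHE's 72% vs the expected 36% also gives 81.6%. Section 6.1 states 81%, so it reproduces, and it concerns efficacy only.

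**Step 2: which observed results pass the safety rule.** With 30 per arm, a active and b sham subjects with SAEs, and m = a + b, the uncorrected statistic reduces to χ² = 60(a − b)² / [m(60 − m)].

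- 3 vs 0: 60 × 9 / (3 × 57) = 3.158, p = 0.076
- 5 vs 1: 60 × 16 / (6 × 54) = 2.963, p = 0.085
- 7 vs 2: 60 × 25 / (9 × 51) = 3.268, p = 0.071

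All three exceed 0.05 and are safe under the rule. They are the largest imbalances that pass for 0, 1 and 2 sham subjects: 4 vs 0 (p = 0.038), 6 vs 1 (p = 0.044) and 8 vs 2 (p = 0.038) would be flagged. For the three examples, p stays between 0.069 and 0.086 for 28 to 32 per arm.

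The Newcombe interval combines the Wilson limits (l, u) of each arm. Its upper limit is d + √[(u₁ − p₁)² + (p₂ − l₂)²], where d = p₁ − p₂.

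| Active vs sham | d | Wilson u₁ | Wilson l₂ | 95% interval for d |
|---|---|---|---|---|
| 3 vs 0 | 10.0% | 25.6% | 0.0% | −3.1% to 25.6% |
| 5 vs 1 | 13.3% | 33.6% | 0.6% | −2.9% to 30.5% |
| 7 vs 2 | 16.7% | 40.9% | 1.9% | −2.0% to 34.9% |

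**Step 3: how often a true excess is called safe.** For each pair of assumed rates, sum Binomial(30, p) probabilities over all tables in which active is not both higher and significant (uncorrected, two-sided 0.05).

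| True excess | Sham vs active | Probability of a safe verdict |
|---|---|---|
| Tripling | 2% vs 6% | 94% |
| Tripling | 5% vs 15% | 74% |
| Tripling | 10% vs 30% | 50% |
| Tripling | 15% vs 45% | 26% |
| Doubling | 5% vs 10% | 90% |
| Doubling | 10% vs 20% | 81% |
| Doubling | 15% vs 30% | 72% |
| Doubling | 20% vs 40% | 61% |

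At 15 per arm, 5% vs 15% would be called safe 91% of the time, against 74% at 30 per arm.

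**Step 4: sensitivity to the form of the test.** Expected SAE subjects per arm in the three examples are 1.5, 3 and 4.5, so the uncorrected approximation is weak and the choice of correction matters. With Yates or Fisher the rule is more lenient: 5 vs 0 (Yates 0.062, Fisher 0.052), 7 vs 1 (0.058, 0.052) and 8 vs 2 (0.083, 0.080) would also pass. The probability of a safe verdict at 5% vs 15% rises to 91%, and at 10% vs 30% to 63%. A one-sided 0.05 uncorrected test would flag the three examples (p = 0.038, 0.043, 0.035). The probability of a safe verdict would then be 61% at 5% vs 15% and 35% at 10% vs 30%.

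**The case against.** The strongest reply has four parts.

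- **Context.** The safety objective in section 3.2 is to record and compare events, and section 6.7.2 puts a summary of events, not the word safe, into future labelling. Section 6.7 tabulates SAEs, UADEs, device-related events and deaths by group, and the DSMB reviews risk against benefit. All of this is true and limits the harm, since a careful reader will see the counts. None of it changes the criterion in section 6.7.1.
- **Sidedness.** The wording of the rule is directional, and under a one-sided uncorrected test all three examples would be flagged. That sensitivity is real, but section 6.5 makes two-sided testing the default and section 6.7.1 notes no exception. One-sided Fisher would still pass all three (p = 0.119, 0.097, 0.073). On either reading, non-significance is still treated as safety.
- **Choice of examples.** The upper limits of 26 to 35 points belong to the most extreme tables that pass. A balanced result gives much less: about 11 points at 0 vs 0 and 15 points at 2 vs 2. The true rates in step 3 are assumptions, and the rule detects a tripling more often as the sham rate rises. The sham rate at which detection becomes more likely than not depends on the form of the test: about 10% for the uncorrected two-sided test. These limits stand and are part of the conclusion.
- **Separate SAP.** Section 6.1 refers to a separate statistical analysis plan for detailed methodology. Its text was not available for this review. The sentence that cites it follows the efficacy analyses, and it may or may not address safety.

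Prior experience does not fill the gap: the NICHE figure counts device-related SAEs only, whereas the rule compares all SAEs.

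**Conclusion.** The concern holds: the decision rule is wrong as written. It commits the trial in advance to a safe conclusion for results that leave an excess SAE risk of about 25 to 35 percentage points unexcluded, and nothing in the protocol text supports that conclusion. The three examples rest on 30 per arm and the two-sided 0.05 test that section 6.5 makes the default; a continuity correction or Fisher's test would let larger imbalances through. The probabilities of a safe verdict also rest on assumed SAE rates. The efficacy analysis is not affected. The change should be made before the safety results are reported.

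**What to change.** Delete the sentence in section 6.7.1 that makes non-significance the criterion for safety. In its place, report the difference in the proportion of subjects with an SAE, active minus sham, in the Safety population, with a 95% score-based (Newcombe) or exact confidence interval. Word the conclusion by the upper limit, as the largest excess SAE risk that the trial has not ruled out. The planned chi-square p-value can stay as description. Any matching text in the separate SAP should be brought into line.

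The cost is a wording change and one interval computed from counts already planned for reporting; no new data, visits or patients are needed. The sponsor loses an automatic safe statement, and the interval will look wide: even with no SAEs in either arm its upper limit is 1.96² / (30 + 1.96²) = 3.84/33.84, about 11 points. That width is what 30 subjects per arm can say about SAEs.

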The beneficial effect of 1Hz NBS guided rTMS will be established if a statistically signicantly greater proportion of patients receiving NBS-rTMS attain clinically important improvement in the primary outcome measure than patients receiving sham-rTMS between baseline and 6 months post-treatment. Minimal clinically important improvement is defined as an increase of 5 points on the upper extremity Fugl-Meyer score [Page SJ, et al. 2012].

Secondary Assessments	1. Secondary outcome measures for the study are:					
and	Arm-Research Action Test (ARAT)					
Endpoints:	NIH Stroke Scale (NIHSS)					

Quality of life assessment: EQ-5D questionnaire.

The changes on these scales between baseline and 6 months post-treatment will be determined for both therapy groups and the groups compared to each other.

2. Safety endpoint

To assess safety of study device use, all Serious Adverse Events and Unanticipated Adverse Device Events and Device Related Adverse Events will be recorded and compared between therapy groups..

ABBREVIATIONS

APB	Abductor Pollicis Brevis
CRO	Clinical Research Organization

EDC	Extensor Digitorum Communis
EMG	Electromyography
FDA	Food and Drug Administration
fMRI	Functional Magnetic Resonance Imaging
IRB	Institutional Review Board
MEP	Motor Evoked Potential
MRI	Magnetic Resonance Imaging
MT	Motor Threshold
NBS	Navigated Brain Stimulation
NBT	Navigated Brain Therapy
rTMS	Repetitive Transcranial Magnetic Stimulation
SAE	Serious Adverse Events
SD	Standard Deviation
TMS	Transcranial Magnetic Stimulation

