3.2 SECONDARY OBJECTIVES

Secondary outcome measures for the study are:

Absolute change in points on UEFM

Action-Research Arm Test (ARAT)

NIH Stroke Scale (NIHSS)

The changes on these scales between baseline and 6 months post-treatment will be determined for both therapy groups and the groups compared to each other to establish effects of therapy.

Quality of life outcomes:

In addition to the other secondary outcome measures above the patients' quality of life will be assessed using the EQ-5D questionnaire. The change on this scale between baseline and 6 months post-treatment will be determined for both therapy groups and the groups compared to each other to establish effects of therapy on quality of life.

Assessment of safety:

To assess safety of study device use, all Serious Adverse Events, Unanticipated Adverse Device Events and Device Related Adverse Events will be recorded and compared between therapy groups..

4.0 study design

This is a prospective multi-center sham-controlled double-blinded study.

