6.7 SAFETY ANALYSES

The Safety Population will be used for all analysis, summaries, and listings of safety data.

Adverse Events

All reported terms (investigator descriptions) for AEs will be coded using the most recent version of the Medical Dictionary for Regulatory Activities (MedDRA v16.0) and summarized with frequencies and percentages by treatment group, system organ classification, and preferred term.

Note that subjects experiencing AEs are counted at most one time per preferred term and at most one time per system organ class, at the highest recorded severity and causality. Events without recorded relationship or causality are summarized as severe or definitely related.

The number and percentage of subjects in the following categories will be summarized by group and overall: subjects with AE, TEAE, SAE, TESAE, UADE, DRAE, TEAE resulting in study discontinuation, and deaths.

The following tables will also be presented:

- All TEAEs
- SAEs and TESAEs
- TEAEs by severity
- TEAEs leading to premature discontinuation of study treatment.

Separate data	listings	W1II	be	presented	for	all	AEs	and	SAES.
---------------	----------	------	----	-----------	-----	-----	-----	-----	-------

Unanticipated Adverse Device Events (UADE)

A UADE is defined as any AE that is definitely related to the study device. All UADEs will be summarized by System Organ Class and Preferred Term. A listing of UADEs will also be provided.

Device-Related Adverse Events (DRAE)

A DRAE is defined as any AE that is possibly, probably, or definitely related to the study device. All DRAEs will be summarized by System Organ Class and Preferred Term. A listing of DRAEs will also be provided.

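### Treatment is declared safe on all-cause SAEs alone, so an excess of non-serious device-related events cannot alter the stated safety conclusion, although the protocol promises to compare those events between arms

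*Combined protocol and SAP*

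**What the plan says.** Section 3.2 (Assessment of safety) commits to a comparison of three classes: "all Serious Adverse Events, Unanticipated Adverse Device Events and Device Related Adverse Events will be recorded and compared between therapy groups". The safety endpoint in the Protocol Summary is the same in substance: "Unanticipated Adverse Device Events and Device Related Adverse Events will be recorded and compared between therapy groups", with SAEs named first.

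Section 6.7 treats the classes differently. For a list of categories that includes SAE, UADE and DRAE, it says: "The number and percentage of subjects in the following categories will be summarized by group and overall". For DRAEs it adds: "All DRAEs will be summarized by System Organ Class and Preferred Term. A listing of DRAEs will also be provided". UADEs get the same summary and listing. No test or interval is named for either.

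Section 6.7.1 holds the only between-group safety test: "Number of subjects with SAEs and TESAEs will be summarized by group and compared using a Chi Square test". It also holds the only criterion for a safety conclusion: "The use of study treatment will be considered safe if the proportion of SAEs in the active rTMS group is not statistically significantly higher" than under sham.

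Section 6.7.2 carries summaries of all three classes into future labelling. Section 2.2 reports the experience of the preceding trial (NICHE): "no device related SAE occurred in the 3448 therapy sessions performed in 199 patients".

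**The concern.** The stated purpose is to assess the safety of using the device, and all three classes are to be compared for that purpose. The conclusion rests on one of them, and that one is counted whatever its cause. In a stroke population, all-cause SAEs include events unrelated to stimulation. DRAEs are the class that isolates device harm, and they have no influence on the verdict.

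The device effects described in section 2.2 include mild headache, skin irritation from electrode paste and transient auditory threshold change. These would usually be non-serious. If they were clearly more frequent under active stimulation, the plan as written could still report the treatment as safe, without the comparison that 3.2 promised. That statement would then stand beside the DRAE summary in labelling.

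The point is which events enter the comparison and the verdict. It is separate from the weakness of treating non-significance as evidence of safety, and it would remain if the SAE test were replaced by a confidence interval.

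**Working it through.** The core of the check is a comparison of texts. The plan states no safety power, margin or expected event rate, so there is no safety figure to reproduce.

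| Class | Protocol Summary and 3.2 | By-group table (6.7) | Test (6.7.1) | Role in the verdict (6.7.1) |
|---|---|---|---|---|
| SAE | compare | yes | chi-square | decides it |
| DRAE | compare | yes | none | none |
| UADE | compare | yes | none | none |

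TESAEs are also tested, but they are a subset of SAEs. Under the definitions in 6.7, a DRAE is an event with a possible, probable or definite device relationship, and a UADE is one with a definite relationship. Every UADE is therefore also a DRAE.

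**Which device events reach the rule.** Section 7.0 defines an SAE by outcome (for example death, threat to life, disability, hospitalisation), whatever the cause. A device-related event that meets this definition is counted in 6.7.1. A non-serious one is not.

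**How likely a device signal is to be serious.** Section 2.2 gives 0 device-related SAEs in 199 patients. The one-sided 95% upper limit is 1 − 0.05^(1/199) = 1.5% of patients. The 199 include sham patients. If only the 88 active patients with ischemic stroke (section 6.1) are counted, the limit is 1 − 0.05^(1/88) = 3.3%. Serious device events have been rare or absent, so a signal is more likely to be non-serious.

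**Illustration of the gap.** Inputs: about 30 patients per arm (5.2.3); two-sided alpha of 0.05 (6.5); assumed SAEs in 1 vs 1 patients; assumed non-serious DRAEs in 12 vs 3 patients.

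- SAE rule: 1/30 vs 1/30 gives chi-square p = 1.00, so the treatment is considered safe.
- DRAE difference: 40% − 10% = 30 points.
- Wilson 95% limits: active 24.6% to 57.7%, sham 3.5% to 25.6%.
- Newcombe lower limit: 30 − √[(40 − 24.6)² + (25.6 − 10)²] = 8.
- Newcombe upper limit: 30 + √[(57.7 − 40)² + (10 − 3.5)²] = 49.
- Uncorrected chi-square = 60 × (12×27 − 3×18)² / (30×30×15×45) = 7.2, p = 0.007 (0.017 with continuity correction). Fisher p = 0.015.

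Other assumed DRAE splits behave the same way:

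| DRAE, active vs sham | Difference (95% CI), points | Fisher p | Conclusion under 6.7.1 if SAEs are 1 vs 1 |
|---|---|---|---|
| 9 vs 2 | 23 (4 to 42) | 0.042 | safe |
| 12 vs 3 | 30 (8 to 49) | 0.015 | safe |
| 15 vs 3 | 40 (17 to 58) | 0.0015 | safe |

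**The case against.** A by-arm table is a comparison in the ordinary sense of a safety section, and 3.2 names no test. A single serious-event criterion with descriptive DRAEs is a defensible design. A DRAE excess would also not go unseen. Under section 7.0 the DSMB assesses every adverse event for relationship to the device, weighs risk against benefit and can recommend changes. Events with no recorded relationship are counted as definitely related. DRAE summaries go into labelling.

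Much of this stands, and it rules out several stronger readings:

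- A reader might infer that UADEs and DRAEs are left out of the between-arm presentation. They are not; 6.7 shows numbers and percentages by group. What is missing is an interval or test and any role in the conclusion.
- A reader might infer that no device-related event can change the verdict. Serious ones can. A seizure or a persistent hearing change may qualify as serious.
- A reader might conclude that device-related SAEs would almost never make the rule fail. With no SAEs in the sham arm, failure needs 4 active patients by uncorrected chi-square (4 vs 0, p = 0.038; 3 vs 0, p = 0.076). At the upper limits above, the chance of 4 or more in 30 is 0.1% or 1.7%. Those probabilities assume no background SAEs, and the documents give no background rate. They also assume the uncorrected test, which 6.7.1 does not specify. With continuity correction or Fisher's test, 6 vs 0 is needed.
- A reader might want one verdict from all three comparisons together. That would need a decision rule and a way to handle the overlap of UADEs with DRAEs. A DRAE excess made up of minor discomfort would not by itself show that the device is unsafe.

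None of this changes the 6.7.1 sentence. The DSMB's assessment and the labelling summaries do not feed into it. The plan also distinguishes the two treatments in its own wording: SAEs are to be summarised and compared, DRAEs only summarised.

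**Conclusion.** The concern holds in a limited form. Two of the three classes that the protocol says it will compare are only tabulated, and the safety conclusion rests on all-cause SAEs. An excess of non-serious device-related events, even one as large as 30 points at 30 per arm, cannot alter that conclusion.

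The mismatch rests on the text alone. The size is an illustration: the DRAE and SAE counts are assumed, and the trial's true rates are unknown. That a device signal would most likely be non-serious rests on the preceding trial's record of no device-related SAE. Section 6.1 refers to a separate statistical analysis plan for the detailed efficacy methods. It is not among the documents reviewed, and if it specifies a DRAE comparison, the protocol should say so.

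The efficacy inference is unaffected. This is a correction worth making to how safety is analysed and worded, and does not show that the device is unsafe.

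**What to change.** In section 6.7.1:

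1. Add a between-arm comparison of patients with at least one DRAE in the Safety Population: the risk difference, active minus sham, with a 95% CI (the Newcombe interval suits 30 per arm). Show patients with a UADE in the same table as the subset they are under the definitions in 6.7.
2. Replace the sentence declaring the treatment safe with one limited to SAEs, such as: no excess of SAEs was shown. Report it alongside the DRAE and UADE difference.

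This brings the analysis into line with the Protocol Summary and 3.2. It needs no composite verdict.

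The cost is protocol and SAP wording and one table from data already collected. The downside for the sponsor is that the safety statement may be less favourable, because active stimulation may produce more minor DRAEs than sham.
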